#### **7.11.4.2 Males**

Pomalidomide is present in the semen of males who take pomalidomide. The effects of MLN9708 are unknown. Therefore, males must always use a latex or synthetic condom during any sexual contact with females of reproductive potential while taking pomalidomide or MLN9708 and for up to 28 days after discontinuing pomalidomide or 90 days after discontinuation of MLN9708, even if they have undergone a successful vasectomy. Male patients taking pomalidomide or MLN9708 must not donate sperm. All study participants must be registered into the mandatory POMALYST REMS™ program, and be willing and able to comply with the requirements of the POMALYST REMS™ program.

### **7.12 Management of Clinical Events**

Adverse drug reactions such as thrombocytopenia, diarrhea, fatigue, nausea, vomiting, and rash have been associated with MLN9708 treatment. Management guidelines regarding these events are outlined below. Further details of management of MLN9708 AEs are described in the MLN9708 IB.

#### Prophylaxis Against Risk of Infection

If lymphopenia is noted, patients may be at an increased risk of infection. In particular, lymphopenia can be associated with reactivation of herpes zoster and herpes simplex viruses. Antiviral therapy such as acyclovir or valacyclovir may be initiated as clinically indicated. Other antivirals are also acceptable.

#### Nausea and/or Vomiting

Standard anti-emetics, including 5-HT3 antagonists, are recommended for emesis occurring upon treatment initiation; prophylactic anti-emetics may also be considered. Dexamethasone should not be administered as an anti-emetic. Fluid deficits should be corrected before initiation of study drug and during treatment.

#### Diarrhea

Diarrhea should be managed according to clinical practice, including the administration of antidiarrheals once infectious causes are excluded. Fluid intake should be maintained to avoid dehydration. Fluid deficits should be corrected before initiation of treatment and during treatment. Prophylactic antidiarrheals are not generally recommended.

### Erythematous Rash With or Without Pruritus

As with VELCADE, rash with or without pruritus has been reported with MLN9708, primarily at the higher doses tested. The rash may range from some erythematous areas, macular and/or small papular bumps that may or may not be pruritic over a few areas of the body or more generalized, has been transient and has resolved either spontaneously or with standard symptomatic measures such as oral or topical steroids and/or antihistamines. Prophylactic measures should also be considered if a patient develops a rash (eg, using a thick, alcohol-free emollient cream on dry areas of the body). In the case of rash, the use of a topical or oral steroid (eg, prednisone  $\leq$  10 mg per day or equivalent) is permitted. A rare risk is Stevens-Johnson Syndrome, a severe, life-threatening or deadly rash with skin peeling and mouth sores, which should be managed symptomatically according to standard medical practice.

### Thrombocytopenia

Thrombocytopenia has been reported to date primarily at the higher doses tested. Blood counts should be monitored regularly as outlined in the protocol with additional testing obtained according to standard clinical practice. Thrombocytopenia may be severe but has been manageable with platelet transfusions according to standard clinical practice. Thrombocytopenia nadirs commonly recover without intervention by the beginning of the next scheduled cycle. MLN9708 administration should be modified as noted as per dose modification recommendations when thrombocytopenia occurs. A rare risk is thrombotic thrombocytopenic purpura (TTP), a rare blood disorder where blood clots form in small blood vessels throughout the body characterized by thrombocytopenia, petechiae, fever, or possibly more serious signs and symptoms. TTP should be managed symptomatically according to standard medical practice.

### Neutropenia

Neutropenia has been reported with MLN9708 and pomalidomide. Blood counts should be monitored regularly as outlined in the protocol with additional testing obtained according to standard clinical practice. Neutropenia may be severe but has been manageable with G-CSF. Neutropenic nadirs commonly recover without intervention by the beginning of the next scheduled cycle or with a short delay in treatment. MLN9708 administration should be modified when neutropenia occurs, as noted in the dose modification recommendations. Given that MLN9708 will be administered in combination with pomalidomide, with overlapping toxicity of neutropenia, G-CSF will be used prophylactically in this protocol.

### Fluid Deficits

Dehydration should be avoided because MLN9708 may cause vomiting, diarrhea, and dehydration. Acute renal failure has been reported with MLN9708. Fluid deficits should be corrected before initiation of study drug and during treatment and as needed during therapy.

Nonsteroidal anti-inflammatory drugs (NSAIDs) induced prevalence of nephrotoxicity is relatively low; however, given the wide use of these agents many persons are at risk, including for example, patients with cardio-renal disease, dehydration, and the aging kidney. NSAIDs should be avoided with impaired renal function given reported NSAID-induced renal failure in patients with decreased renal function. Until further information is available, intake of NSAIDs while on this protocol should be avoided.

### Hypotension

Symptomatic hypotension and orthostatic hypotension have been reported with MLN9708. Blood pressure should be closely monitored while the patient is on study treatment and fluid deficit should be corrected as needed, especially in the setting of concomitant symptoms such as nausea, vomiting, diarrhea, or anorexia. Patients taking medications and/or diuretics to manage their blood pressure (for either hypo- or hypertension) should be managed according to standard clinical practice, including considerations for dose adjustments of their concomitant medications during the course of the trial.

### Posterior Reversible Encephalopathy Syndrome

One case of posterior reversible encephalopathy syndrome (PRES) has been reported with MLN9708. While this case ultimately resolved, PRES has also been reported rarely with another proteasome inhibitor, Velcade. PRES is characterized by headache, seizures and visual loss, as well as abrupt increase in blood pressure. Prompt diagnosis and initiation of antihypertensive and anticonvulsant therapy are important to prevent irreversible end-organ damage.

### Anticoagulation Consideration

Pomalidomide increases the risk of thrombotic events in patients who are at high risk or with a history a thrombosis, in particular when combined with other drugs known to cause thrombosis.

Consideration should be given to the requirement of aspirin (81 or 325 mg) or some other form of prophylaxis as deemed appropriate. Low molecular weight heparin may be utilized in patients that are intolerant to ASA. Coumadin should be used with caution and close monitoring of INR.

## **8. STUDY DRUG**

### **8.1 Packaging and Labeling**

#### **8.1.1 MLN9708**

The study drug MLN9708 capsules will be provided by Millennium. The study drug will be labeled and handled as open-label material, and packaging labels will fulfill all requirements specified by governing regulations.

MLN9708 capsules should be stored unopened at 2°C to 8°C (36°F-46°F). The capsules are individually packaged in cold form foil-foil blisters in a child-resistant package. The 0.5-, 2.3-, 3.0-, and 4.0 mg capsules are supplied as a 1 x 3 blister card in a child-resistant cardboard wallet.

#### **8.1.2 Pomalidomide**

Pomalidomide capsules will be provided by Celgene Corporation as 1.0, 2.0, 3.0 and 4.0 mg capsules for oral administration.

Pomalidomide (POMALYST®) will be provided to research patients for the duration of their participation in this trial at no charge to them or their insurance providers. Pomalidomide will be provided in accordance with the Celgene Corporation's POMALYST REMST™ program. Per the standard POMALYST REMST™ program requirements, all physicians who prescribe pomalidomide for research patients enrolled into this trial, and all research patients enrolled into this trial, must be registered in and must comply with all requirements of the POMALYST REMST™ program.

Drug will be shipped on a per patient basis by the contract pharmacy to the clinic site for IND studies. Only enough pomalidomide for one cycle of therapy will be supplied to the patient each cycle. This is in accordance with the POMALYST REMST™ program.

Pomalidomide investigational supplies are dispensed to the patients in individual bottles of capsules. Each bottle will identify the contents as study medication. In addition, the label will bear Celgene's name, quantity contained and the standard caution statement as follows: Caution: New drug - Limited by Federal law to investigational use. Pomalidomide should not be

handled by FCBP unless wearing gloves. All bottles will contain the following warning label: “WARNING: POTENTIAL FOR HUMAN BIRTH DEFECTS.”

The study drug label must be clearly visible. Additional labels must not cover the Celgene label.

## **8.2 Storage, Handling, and Accountability**

MLN9708 and pomalidomide are anticancer drugs and as with other potentially toxic compounds caution should be exercised when handling MLN9708 and pomalidomide capsules.

### **8.2.1 MLN9708**

Upon receipt at the investigative site, MLN9708 should remain in the blister and carton provided until use or until drug is dispensed. The container should be stored at the investigative site refrigerated (36°F to 46°F, 2°C to 8°C). Ensure that the drug is used before the retest expiry date provided by Millennium. Expiry extensions will be communicated accordingly with updated documentation to support the extended shelf life.

In countries where local regulations permit, MLN9708 capsules dispensed to the patient for take-home dosing should remain in the blister packaging and refrigerated as noted above until the point of use. The investigative site is responsible for providing the medication to the patient in the correct daily dose configurations. Comprehensive instructions should be provided to the patient in order to ensure compliance with dosing procedures. Patients who are receiving take-home medication should be given only 1 cycle of medication at a time. Patients should be instructed to store the medication refrigerated (36°F to 46°F, 2°C to 8°C) for the duration of each cycle. Patients should be instructed to return their empty blister packs to the investigative site, rather than discarding them. Reconciliation will occur accordingly when the patient returns for their next cycle of take-home medication. Any extreme in temperature should be reported as an excursion and should be dealt with on a case-by-case basis.

Because MLN9708 is an investigational agent, it should be handled with due care. Patients should be instructed not to chew, break, or open capsules. In case of contact with broken capsules, raising dust should be avoided during the clean-up operation. The product may be harmful by inhalation, ingestion, or skin absorption. Gloves and protective clothing should be worn during cleanup and return of broken capsules and powder to minimize skin contact.

The area should be ventilated and the site washed with soap and water after material pick-up is complete. The material should be disposed of as hazardous medical waste in compliance with federal, state, and local regulations.

In case of contact with the powder (eg, from a broken capsule), skin should be washed immediately with soap and copious amounts of water for at least 15 minutes. In case of contact with the eyes, copious amounts of water should be used to flush the eyes for at least 15 minutes. Medical personnel should be notified. Patients are to be instructed on proper storage, accountability, and administration of MLN9708, including that MLN9708 is to be taken as intact capsules.

Investigational MLN9708 (expired or end of study) should be destroyed on site according to the institution's standard operating procedure. Be sure to document removal and destruction on drug accountability logs.

### **8.2.2 Pomalidomide**

Care should be exercised in handling of pomalidomide. Pomalidomide capsules should not be opened or crushed. If powder from pomalidomide contacts the skin, wash the skin immediately and thoroughly with soap and water. If pomalidomide contacts the mucous membranes, flush thoroughly with water.

The Investigator or designee is responsible for taking an inventory of each shipment of pomalidomide received, and comparing it with the accompanying study drug accountability form. The Investigator or designee will verify the accuracy of the information on the form, sign and date it, retain a copy in the study file, and return a copy to Celgene or its representative.

#### **Storage**

At the study site, all pomalidomide will be stored in a locked, safe area to prevent unauthorized access. The study drug should be stored at room temperature away from direct sunlight and protected from excessive heat and cold.

#### **Unused study drug supplies**

Celgene will instruct the Investigator or designee on the return or destruction of unused pomalidomide. If any pomalidomide is lost or damaged, its disposition should be documented in the source documents. Pomalidomide supplies will be retained at the clinical site pending instructions for disposition by Celgene. Patients will be instructed to return empty bottles or unused capsules.

**Only enough pomalidomide capsules for 1 cycle of therapy may be provided to the patient**  
**Confidential**

each cycle.

## 9. STUDY COMPLIANCE

Study drug will be administered or dispensed only to eligible patients under the supervision of the investigator or identified sub-investigator(s). The appropriate study personnel will maintain records of study drug receipt and dispensing.

### 9.1 Treatment Assignment

Patients will be assigned at the time of enrollment (per section 6.0) to a given dose level during the phase I portion of the study or to the recommended phase II dose as determined during the phase I portion of the study.

### 9.2 Termination of Treatment and/or Study Participation

Patients will be informed that they have the right to withdraw from the study at any time for any reason, without prejudice to their medical care. The investigator also has the right to withdraw patients from the study for any of the following reasons:

- Adverse event
- Lack of Protocol adherence
- Lost to follow-up
- Progressive disease
- Study termination

At the time of withdrawal, all study procedures outlined for the End of Treatment visit should be completed. The primary reason for patient's withdrawal from the study will be recorded in the source documents and CRF.

The Lead Principal Investigator or designee must be notified within 24 hours if a patient is withdrawn from the study by the Data Coordinating Center or designee.

If the reason for withdrawal is the occurrence of an AE, the Investigator will follow the patient until such events resolve, stabilize, and according to the Investigator's judgment, there is no need of further follow up.

## 10. STATISTICAL AND QUANTITATIVE ANALYSES

### 10.1 Statistical Methods

#### 10.1.1 Determination of Sample Size

**Phase I:** The phase I study will follow a 3+3 design, to evaluate toxicities associated with MLN9708 when given in combination with pomalidomide and dexamethasone. Two doses of MLN9708 (dose level -1 and dose level 1: 3 mg; dose level 2: 4 mg) will be tested in up to three possible dose levels; there will be no dose reductions below the 3mg dose of MLN9708. In the phase I portion of this study, the total sample size will depend on the number of dose levels evaluated to determine the maximum tolerated dose (MTD). While the phase I study is expected to enroll and treat 9 patients (3 patients treated on dose level 1 and 6 additional patients treated at dose level 2 -assuming the 4mg dose is well tolerated), a maximum of 18 patients could be treated (6 patients per dose level). The highest dose level that produces  $\leq 1/6$  DLTs in cycle 1 will be the MTD. (See section 7.4 for dose expansion/escalation rules.) The recommended phase II dose (RP2D) of MLN9708 and pomalidomide will generally be the MTD, but it may be less than the MTD based on a review of available data/cumulative toxicities from phase I.

**Phase II:** For this trial, where MLN9708 will be added to pomalidomide and dexamethasone, patients with prior exposure to either of these agents would not be excluded, unlike the patients treated on the randomized phase III study of comparing pomalidomide plus dexamethasone, to high-dose dexamethasone alone. As many patients (>50%) are likely to have been previously treated with one or both of these agents we consider a response rate of 30% sufficient efficacy to justify further development. In addition, the estimation of response in this refractory/high-risk population is of equal importance. Given this, the phase II portion of the trial, will use a Gehan two stage design (Gehan, 1961). The phase II trial is expected to enroll a minimum of 9 and a maximum of 25 patients. The six patients treated at the RP2D in the phase I portion of the study will count toward the 25 patients required. Given this, we expect to enroll only 19 new patients on the phase II trial. The sample size is based on the desire to estimate the response rate with at most 10% standard error, and early stopping if the combination is unexpectedly ineffective. The primary endpoint is confirmed tumor response (sCR/CR/VGPR or PR).

At stage 1, 9 patients will be entered on the study. If 0 responses are seen in the first 9 patients treated, the study will be terminated and the true regimen response will be declared  $\leq 30\%$ . If at least 1 patient responds, the trial will continue to the second stage. Because patients treated during the phase I portion of the trial at the dose selected for the phase II trial will be counted

(n=6), only 3 additional patients will be enrolled at stage 1. Under this design if the study regimen is >30% effective, there would be ~95.6% chance of at least one success. At stage 2, 16 additional patients will be entered. This accrual provides for estimation of the response rate with no more than 10% standard error.

#### **10.1.2 Populations for Analysis**

**Phase I (Evaluable for Toxicity):** Patients will be considered evaluable for toxicity if they receive any study drug. Patients will be considered evaluable for dose limiting toxicity if they receive at least 75% of both Pomalidomide and MLN9708 and are followed for the full 28 days during cycle 1 or experience a DLT. All patients who are not evaluable for dose limiting toxicity will be replaced.

**Phase II (Evaluable for Toxicity):** Patients will be considered evaluable for toxicity if they receive any study drug. Patients in Phase II will not be replaced based on toxicity.

**Phase I and II (Evaluable for Response):** For the phase II portion, as part of the primary analysis, patients will be considered evaluable for response if they are eligible, have baseline disease assessments, and receive any protocol treatment. As part of a secondary analysis, patients will be considered evaluable for response if they have baseline disease assessments, receive at least 75% of both Pomalidomide and MLN9708 during the first cycle of therapy and have had their disease re-evaluated. Patients will have their response classified according to the IMWG response criteria. All patients in phase II and those treated at the RP2D in phase I, who are not evaluable for response will be replaced.

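### Does the response-replacement rule in section 10.1.2 need to say which definition of evaluable it uses?

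*Combined protocol and SAP*

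**What the plan says.** The paragraph on response evaluability in section 10.1.2 gives two definitions. For the primary analysis, "patients will be considered evaluable for response if they are eligible, have baseline disease assessments, and receive any protocol treatment". For a secondary analysis, patients must have a baseline assessment, "receive at least 75% of both Pomalidomide and MLN9708 during the first cycle of therapy and have had their disease re-evaluated". A sentence on IMWG classification comes next, and then the replacement rule: "All patients in phase II and those treated at the RP2D in phase I, who are not evaluable for response will be replaced". Section 7.7 repeats both definitions and has no replacement rule. The combined file contains the protocol text twice, with the same wording here.

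The toxicity paragraphs of section 10.1.2 have replacement rules of their own. For phase I: "All patients who are not evaluable for dose limiting toxicity will be replaced". For phase II: "Patients in Phase II will not be replaced based on toxicity".

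Section 10.1.1 gives the counts: "The phase II trial is expected to enroll a minimum of 9 and a maximum of 25 patients". Six of these come from phase I at the recommended dose, so "only 3 additional patients will be enrolled at stage 1", and 16 more follow at stage 2. On precision it says: "This accrual provides for estimation of the response rate with no more than 10% standard error".

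**The concern.** A rule that triggers enrolment should say what sets it off, and this one follows two definitions without naming either.

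There is something to be said for the stricter reading. It is the later of the two definitions. The rule also reaches back to phase I patients already treated at the recommended dose. Under the primary definition such a patient could fail only by proving ineligible or lacking a baseline assessment, and section 6 has the coordinating center verify eligibility before registration. A site could therefore apply the 75% test in good faith.

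That reading sits badly with other parts of the plan. Section 7.9.1 says that a held Day 8 or Day 15 MLN9708 dose is omitted, so one toxicity hold in cycle 1 would lead to replacement, although phase II patients are not to be replaced for toxicity. The carry-over of six and the total of 25 would no longer be firm. If none of the first nine treated patients responded and one of them had failed the 75% test, section 10.1.1 would end the trial while the replacement rule asked for another patient. What is at stake is the number of patients exposed, and possibly who is counted at stage 1.

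**Working it through.** **1. The plan's own figures.** Inputs from section 10.1.1: 9 patients at stage 1, target response rate 30%, 25 patients in all, 6 carried over.

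- Chance of at least one response in 9 at 30%: 1 − 0.7^9 = 1 − 0.0404 = 0.9596, or 96.0%. The plan says about 95.6%, which is close enough.
- Largest standard error at n = 25: √(0.25/25) = 10.0%. At a 30% rate: √(0.21/25) = 9.2%. The target of at most 10% is met.
- Counts: 9 − 6 = 3 new at stage 1; 25 − 9 = 16 at stage 2; 25 − 6 = 19 new in all. These agree with the plan.

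**2. Which reading fits.** Under the primary definition every count above stands, apart from replacing the occasional patient found ineligible or without a baseline assessment. Under the secondary definition:

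- 75% of 3 MLN9708 doses is 2.25, so all three are needed; two of three is 66.7%.
- Selection of the maximum tolerated dose allows one dose-limiting toxicity in six. If that patient had a dose held, the carry-over becomes 5, stage 1 needs 4 new patients, and new enrolment is 4 + 16 = 20. The plan has 6, 3 and 19.

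The stage 1 stopping rule is also written in terms of patients treated, which matches the primary definition.

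**3. Does the primary result depend on the reading?** No. A patient who fails only the 75% or re-evaluation test still meets the primary definition and stays in the primary denominator, replaced or not. Extra enrolment would only enlarge that set: the largest standard error is √(0.25/28) = 9.4% at 28 patients and √(0.25/30) = 9.1% at 30.

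**4. Size of the accrual effect under the stricter reading.** The documents give no failure rate, so f = 4%, 10% and 15% are assumptions. Applying f to all 25 patients overstates the effect. The six carried-over patients must be evaluable for dose-limiting toxicity, which means at least 75% of both drugs or a dose-limiting toxicity, and at most one of the six may have had one. At least five therefore pass the dose test. Assuming that those who pass it were also re-evaluated:

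| f for new patients | all six pass: 6 + 19/(1 − f) | one of six fails: 6 + 20/(1 − f) |
|---|---|---|
| 4% | 25.8 | 26.8 |
| 10% | 27.1 | 28.2 |
| 15% | 28.4 | 29.5 |

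That is 0.8 to 4.5 patients above 25 on average.

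**5. The secondary analysis without top-up.** With 25 treated and the same f range, 25 × 0.96 = 24.0 or 25 × 0.85 = 21.25 patients remain. The largest standard error is √(0.25/24) = 10.2% or √(0.25/21.25) = 10.8%, a small loss in a supporting analysis.

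**6. Phase I patients replaced for toxicity evaluability.** Suppose m extra patients were treated at the recommended dose for this reason. Section 10.1.1 already says that phase I patients treated at the chosen dose are counted; six is the number expected. The total is then (6 + m) + (3 − m) + 16 = 25, with 19 − m new patients: 18 for m = 1, 17 for m = 2. No added rule is needed.

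**The case for a change.** The best case for a change is that the sentence decides how many patients receive an investigational combination, that both readings can be argued from the page, and that a clarification costs a few words. The point about wording stands: neither definition is named, and section 7.7 does not help.

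The rest weakens on inspection. The replacement sentence does not directly follow the secondary definition; a sentence that applies to every patient comes between. Naming the phase I patients makes sense under the primary definition, because they count toward the 25 and one later found ineligible would need replacing. The statement against replacing phase II patients for toxicity sits in the toxicity-evaluability paragraph, opposite the phase I rule on dose-limiting toxicity, and may concern only that kind of evaluability. The conflict with it is therefore possible rather than certain. The 25 and the 19 are introduced as expectations, and any replacement rule, including one on the primary definition, can move them.

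A rule holding the number treated at exactly 25 would bring a new difficulty, since it could clash with replacing a treated patient who proves ineligible.

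**Conclusion.** This is a gap in wording that the trial team can fill from the rest of the plan. The primary definition agrees with the carry-over of six, the three and sixteen new patients, and a stage 1 rule that counts treated patients. It is very probably what was meant. A team that follows it obtains the stated design: 96.0% against about 95.6% at stage 1, and a standard error of at most 10.0%.

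If someone took the stricter reading, the primary estimate and its denominator would still be defined as written. The cost would be some extra accrual: about 1 to 5 patients if 4% to 15% of new patients failed the secondary definition. Those rates are assumptions, so the true size cannot be computed from the documents. The disagreement between stopping and replacing at stage 1 needs no response in nine treated patients, which has a chance of 0.7^9 = 4.0% at a 30% response rate, together with a patient who failed the 75% test. The plan's reference to treated patients settles that case in favour of stopping.

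The conclusion rests on the primary definition governing replacement and on replaced patients who meet it staying in the primary analysis. Both follow from the text, and no change is called for.
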